### 3.3. SAMPLE SIZE

At each site, study areas were selected to correspond to an approximate minimum population of 80,000 to 100,000 people. The study sites were divided into 40 total clusters, 20 in the intervention arm (twice-annual community-wide MDA) and 20 in the control arm (targeted MDA). Cluster sizes vary according to administrative and / or geographic barriers but had a minimum size of 1,650 residents on the baseline census. The minimum cluster size was selected to reduce the probability of repeatedly sampling the same individuals at all three time points to <10%, allowing for 10% refusal rate and the exclusion of the Longitudinal Monitoring Cohort from the sampled population. Randomization of clusters to community-wide vs. school-age targeted MDA was performed within each site as above (Section 3.2.2).

Cross-sectional prevalence surveys at baseline and 6 months post-MDA will be conducted on a random sample of 500 individuals per cluster. The primary outcome assessment of prevalence at 24 months post-MDA will sample 1,000 people per cluster in order to precisely assess prevalence on a cluster-by-cluster basis.

#### 3.3.1 Sample size calculations for Primary Objectives

**Objective 1.1** To compare the prevalence of the predominant STH species (*A. lumbricoides*, *A. duodenale*, *N. americanus* or *T. trichiura*) as measured by quantitative PCR 24 months after stopping MDA between clusters randomized to receive twice-yearly community-wide MDA versus clusters randomized to receive standard of care pre-SAC and SAC targeted MDA.

Power calculations for a range of scenarios were conducted. The following formula outlined by Hayes and Moulton [17]:

$$c = 1 + (Z_{\alpha/2} + Z_{\beta})^2 \frac{[\pi_0(1 - \pi_0) + \pi_1(1 - \pi_1)][1 + (m - 1)\rho]}{m(\pi_0 - \pi_1)^2}$$

was used to calculate the prevalence in the control clusters ( $\pi_0$ ) that would enable detection of a difference between arms with 80% power, given an endline prevalence in the intervention clusters ( $\pi_1$ ) of 2% and a range of assumptions of intraccluster correlation coefficient ( $\rho = 0.003$  to  $\rho = 0.005$ ), number of clusters per arm ( $c = 15$  to  $c = 20$ ) and number of people sampled per cluster ( $m = 500$  or  $m = 1,000$ ), assuming  $\alpha=0.05$ . The detectable alternative  $\pi_0$  ranged from 3% to 3.5%.

Power to detect differences in final prevalence between arms given plausible values for  $\pi_0$ , ranging from 7% to 10% (comparable to pre-intervention prevalences in each of the study sites), was then estimated using simulations conducted in R (R Center for Statistical Computing, Vienna, Austria). Each simulation assumed 1,000 individuals per cluster and a binomial distribution of STH prevalence with a mean of 2% in the intervention clusters and  $\pi_0$  in the targeted arm, a range of ICC and  $\alpha=0.05$ ; 10,000 repetitions were run for each scenario. Power was  $\geq 98\%$  for all scenarios simulated.

**Objective 1.2** To determine whether the transmission of the predominant STH species (*A. lumbricoides*, *A. duodenale*, *N. americanus* or *T. trichiura*) can be interrupted using MDA with albendazole.

Transmission interruption will be assessed at the cluster level and is defined as reaching a weighted point prevalence of  $\leq 2\%$  of that species as measured by quantitative PCR 24 months after stopping MDA. The proportion of clusters randomized to twice-yearly community-wide MDA versus standard of care pre-SAC and SAC-targeted MDA that interrupt transmission will be compared.

Power to detect transmission interruption and differences by arm was also estimated using simulation in R. The threshold for transmission interruption was set at 2.0% prevalence, and a cluster was considered to have interrupted transmission if prevalence could be declared to be below the threshold with 95% confidence, using a one-sided binomial test. Simulations estimated power to detect a difference in the proportion of clusters in which transmission was interrupted by arm.

### Hypothesis 1.2 A

#### Assessment of transmission interruption in each individual cluster $i$

$$H_0: \pi_i \geq 2\%$$

$$H_A: \pi_i < 2\%$$

### Hypothesis 1.2 B

[figure not shown]
#### Between-arm comparison of the proportion of clusters in which transmission has been interrupted

$$H_0: p_0 = p_1$$

$$H_A: p_0 \neq p_1$$

Simulations assumed 20 clusters per arm, 500 or 1,000 individuals per cluster ( $m$ ), and a binomial distribution of STH prevalence with a mean of 7% across clusters in the targeted arm ( $\pi_0$ ) and  $\pi_1$  in the intervention arm, a range of ICC ( $\rho = 0.003$  or  $\rho = 0.005$ ), and  $\alpha=0.05$ ; 10,000 repetitions were run for each scenario.

For a fixed mean endline prevalence of 7% in the targeted arm ( $\pi_0$ ), power to detect a difference in the proportion of clusters eliminated varies by number of individuals sampled per cluster, ICC and endline prevalence in the intervention arm ( $\pi_1$ ), as shown in Figure 1.

**Figure 1:** Power to detect a difference in the proportion of clusters achieving transmission interruption (Primary Objective 2.2.2) assuming 7% mean prevalence in the targeted clusters ( $\pi_0$ ), by mean endline prevalence in the intervention clusters ( $\pi_1$ ), intracluster correlation (ICC) and number of people measured per cluster ( $m$ ), estimated by simulation.

These power calculations demonstrate that with 20 clusters per arm, measuring STH infection among 1,000 people per cluster at endline would provide adequate power for the primary objectives in most scenarios.

## SECTION 4: STATISTICAL PRINCIPLES

### 4.1 CONFIDENCE INTERVALS AND P VALUES

Descriptive statistics will be presented as counts and percentages for binary, ordinal and categorical variables, and as means and standard deviations or medians and interquartile ranges for continuous variables, as appropriate based on distributions. Prevalences will use the finite population correction to account for the large proportion sampled from each cluster, and will be presented with logit Wald confidence intervals.

P-values of  $<0.05$  will indicate statistical significance for all analyses.

### 4.2 ADHERENCE AND PROTOCOL DEVIATIONS

Adherence to the protocol is measured at both the cluster and individual levels. Adherence at the cluster-level refers to rounds of community-wide MDA in the intervention arm, reaching all communities in intervention clusters, being conducted according to the trial schedule laid out by each site.

Individual-level adherence refers to coverage, reach and uptake of MDA among the targeted population: school-age and preschool-age children in the standard of care arm and all age groups eligible in the intervention arm (Table 1). Coverage, reach and uptake are measured using individual treatment logs based on the most recent census in the intervention arm, and using self-report on coverage surveys in both arms (Figure 2).

Each round of MDA in the intervention arm has a target coverage and uptake of 80% of eligible study participants.

Protocol deviations, including missed or rescheduled rounds of MDA and reassignment of households or communities from one cluster to another, are documented in a Protocol Deviations Log and reviewed twice annually during DeWorm3 Data Safety and Monitoring Committee (DSMC) meetings.

Per protocol coverage Treatment logs	Directly observed Tx Treatment logs	Treatment uptake Treatment logs	Self-reported coverage Coverage Survey
Number of censused, eligible cluster residents treated Number of censused, eligible cluster residents	Number of censused, eligible cluster residents directly observed taking treatment Number of censused, eligible cluster residents not recently treated	Number of censused, eligible cluster residents treated Number of censused, eligible cluster residents reached during MDA	Number of surveyed individuals reporting swallowing a tablet Number of surveyed individuals
Population coverage Treatment logs	Non-migratory coverage Treatment logs	Pediatric coverage Treatment logs	
Number of individuals treated Number of censused, eligible cluster residents + those newly encountered during MDA	Number of censused, eligible non-migratory individuals treated Number of censused, eligible non-migratory cluster residents	Number of censused, eligible children treated Number of censused, eligible resident children	

Figure 2: Treatment coverage definitions employed in DeWorm3.

### 4.3 ANALYSIS POPULATIONS

Analysis of DeWorm3 primary objectives will be intention-to-treat according to cluster randomization. All clusters will be considered intervention or control clusters as randomized. All residents of study clusters included on the final census will be eligible for inclusion in endline prevalence assessments and for the primary analyses will be considered exposed or unexposed based on cluster randomization, regardless of their own treatment histories.

## SECTION 5: TRIAL POPULATION

### 5.1 ELIGIBILITY

All individuals residing in households within the study clusters will be considered part of the study population and included in the DeWorm3 baseline census and annual census updates. Cluster residents will be eligible for treatment during MDA in accordance with national guidelines at each site (Table 1). All individuals aged 1 year or older at the time of data collection (2 years or older in Malawi) will be eligible for inclusion in prevalence surveys conducted prior to the first round of MDA (Baseline), 6 months following the final round of MDA (Midline) and 24 months following the final round of MDA (Endline).

### 5.2 RECRUITMENT

Censuses of all individuals residing within the boundaries of each study area will be performed through door-to-door visits. Up to three attempts will be made to reach each household for inclusion in each round of the census. GPS coordinates of all dwellings, unoccupied and occupied, will be collected. The head of household, or other adult comfortable making decisions on behalf of the household, will be asked to provide consent for

inclusion in the census. Household characteristics and basic sociodemographic information on the inhabitants of each household will be collected through a survey.

The most recent census or census update will be used as a sampling frame for each round of the cross-sectional survey. Eligible participants will be randomly selected, stratified by cluster, for inclusion on a sampling list. Participants will be approached at their households and asked to participate in an in-depth survey and provide a stool sample. Adult participants will provide informed consent for their own or their children's participation, while children will provide assent, according to age guidelines in each country. Up to three attempts will be made to reach and recruit each participant on the sampling list. Data collectors will exhaust attempts to recruit individuals on the original sampling list for each cluster before being provided with supplementary lists as needed to reach the target sample size.

### 5.3 WITHDRAWAL

Consent for inclusion in MDA or data collection may be withdrawn during the study. Only a head of household, or the adult who originally provided consent on behalf of the household for inclusion in the census, may withdraw the entire household's consent for inclusion in the census updates and sampling lists. Individual adults may withdraw consent for their own participation in MDA or data collection activities.

### 5.4 BASELINE CHARACTERISTICS

Baseline characteristics collected during the DeWorm3 baseline census of all households in the study area in each site will be summarized at the site, cluster, household and individual levels (Table 4). Cluster-level variables will include those used in the restricted randomization (Table 2).

**Table 4** Results of the DeWorm3 baseline census

Study site characteristics	India	Malawi	Benin
	N (%)	N (%)	N (%)
Geographic area of study site (km  )			
Total number of households			
Population density			
<50 persons/km 			
50-249 persons/km 			
250-999 persons/km 			
≥1000+ persons/km 			
Missing			
Household characteristics	N=	N=	N=
	n (%) / median (IQR)	n (%) / median (IQR)	n (%) / median (IQR)
Household size			
Owner-occupied dwelling			
Wall materials			
-Natural			
-Manmade			
-Other / don't know / refused			
Roofing materials			
-Natural			
-Manmade			
-Other / don't know / refused			
Flooring materials			
-Natural			
-Manmade			
-Other / don't know / refused			
WASH access			
-Sanitation			
-Basic facilities			
-Limited facilities			
-Unimproved facilities			
-No facilities (open defecation)			
-Drinking water source			
-Basic			

-Limited -Unimproved -Surface water					
Study population	N=	N=	N=		
Female					
Age distribution					
-Infants (<1 years) -Preschool-age children (1-4 years) -School age children (5-14 years) -Adults (15+ years) -Missing					
Education (school-aged children)					
-Attending school -Not attending school -Missing					
Highest level of education (adults)					
-No education -Incomplete primary school -Complete primary school -Some secondary school -Greater than secondary school -Missing / don't know / refused					
Migration					
-Lived outside the household the majority of the past 6 months -Slept elsewhere the night before the census					

## SECTION 6: ANALYSIS

### 6.1 OUTCOME DEFINITIONS

The outcomes will be a) individual-level STH infection, defined as an individual's test result for the predominant STH (Objective 1.1) or any STH (Objective 2.1), and b) cluster-level transmission interruption, defined as a prevalence of the predominant STH species (Objective 1.2) or each STH species prevalent at baseline (Objective 2.2) of  $\leq 2\%$  with 95% confidence using a one-sided binomial test, as measured by qPCR 24 months after the final round of MDA.

We will classify each individual's infection status as negative (no amplification, Cycle threshold  $>40$ ), positive, or indeterminate; primary analyses will consider indeterminate results negative, while sensitivity analyses will recategorize indeterminate results as positive. Cycle thresholds indicating a positive or indeterminate result for each species will be defined and standardized by the DeWorm3 STH Molecular Support Unit.

### 6.2 ANALYSIS METHODS

All analyses will be conducted separately for each site, unless otherwise specified.

#### 6.2.1 Analysis of primary objectives

The effect of the primary exposure on endline infection with the predominant STH species at each site (Objective 1.1) will be analyzed using generalized estimating equations with Poisson family, with robust variance estimation and exchangeable correlation matrix. The primary exposure variable will be randomization arm, while the primary outcome will be individual-level STH infection status by qPCR (see Section 6.1).

Models will be adjusted for individual- and cluster-level covariates listed in Table 5. In the primary analyses, these data will be analyzed separately by site, while a secondary analysis will pool data across all sites and test for effect modification using an interaction term between study site and randomization arm.

**Table 5.** Individual- and cluster-level factors to be adjusted for in analysis of Objective 1.1.

Variable	Format	Data source
Cluster baseline age and gender-weighted STH prevalence	Continuous	LMC1 + CSS1
Population density within 0.5km of household	Continuous	Census 5
Household asset index quintile	Ordinal	Census 5
Water source Joint Monitoring Programme (JMP) classification	Ordinal	Census 5
Sanitation facilities JMP classification	Ordinal	Census 5
Hygiene facilities JMP classification	Ordinal	Census 5
Participant age	Continuous	Census 5
Participant gender	Categorical	Census 5
Household size	Continuous	Census 5
Migratory status	Binary	Census 5

The second primary objective of transmission interruption by cluster (Objective 1.2) will be defined as achieving an age- and gender-weighted cluster prevalence  $\leq 2\%$  of the predominant STH species by qPCR 24 months after the final round of MDA. The effect of the primary exposure on transmission interruption will be calculated by comparing the proportion of clusters in each arm in which transmission is successfully interrupted using a Fisher's exact test. In a sensitivity analysis, the proportion of clusters in which transmission is successfully interrupted will be compared using a weighted Chi test to account for sample size contributed by cluster in case not all clusters reach enrollment targets.

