7. STATISTICAL ANALYSIS PLAN

All analyses will be conducted separately for each site, unless otherwise specified.

Primary objectives

The effect of the primary exposure on endline infection with the predominant STH species driving transmission in each site (Objective 2.1.1) will be analysed using generalized estimating equations with binomial family and exchangeable correlation matrix. The primary exposure variable will be randomisation arm, while the primary outcome will be individual-level STH infection status (positive or negative for the dominant species driving transmission species by qPCR). Models may be adjusted for baseline cluster-level STH prevalence and urban/rural designation, socioeconomic status (SES), water sanitation and hygiene (WASH) access, age, gender of the participant, household size, or other relevant variables as appropriate. In the primary analysis, these data will be analysed separately by site, while a secondary analysis will pool all data and test for effect modification using an interaction term between study site and randomisation arm.

Transmission interruption in a cluster (Objective 2.1.2) will be defined as achieving a cluster prevalence $\leq 2\%$ of the dominant STH species driving transmission at each site by qPCR 24 months after the final round of MDA. The effect of the primary exposure on the proportion of clusters in which transmission is successfully interrupted will be calculated by comparing the proportion of clusters in each arm in which transmission is successfully interrupted using a chi-squared test.

Secondary objectives

The effect of randomisation arm on endline infection with each individual species of STH (2.2.1), on the proportion of clusters interrupting transmission of each individual species (2.2.2), on endline infection with any STH species among children (2.2.2) and on shedding of fertilized *Ascaris* eggs (2.2.3) will be analysed using generalized estimating equations with binomial family and exchangeable correlation matrix or chi-squared tests, as detailed above. Models may be adjusted for baseline cluster-level STH prevalence and urban/rural designation, SES, WASH access, age, gender of the participant, household size, or other relevant variables as appropriate.

Secondary analyses

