### 3. STUDY METHODS

#### 3.1 TRIAL DESIGN

DeWorm3 is a multi-site community cluster randomized trial conducted in focal geographic areas in Benin, India and Malawi. At each site, 40 clusters are randomized to receive either three years of twice-annual community-wide mass drug administration (MDA) with albendazole, targeting all age groups, or the current standard of care targeted MDA strategy at the site (Table 1).

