#### 3.2 RANDOMIZATION

Within each DeWorm3 study area, clusters will be randomly assigned in a 1:1 allocation ratio to either community-wide or standard of care MDA (Table 1). Restricted randomization will be performed to ensure balance of baseline factors by arm within each country, and stratified by region in India (Jawadhu Hills, n=8 vs. Thimiri, n=32).

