### 3.2.2 Cluster randomization

Clusters were randomized to community-wide versus targeted MDA stratified by country. Within each country, restricted randomization was performed to ensure balance between arms in baseline population and in factors hypothesized to be strongly associated with STH transmission intensity.

*The protocol for restricted randomization was as follows:*

Factors considered as part of the restricted randomization are age distribution, socio-economic status (SES), WASH access, urban / rural designation of clusters, and baseline STH prevalence as measured by Kato-Katz. Operationally, these factors and balancing criteria are defined as shown in Table 2.

Restricted randomization will be performed in Stata (StataCorp, College Station, Texas). Simulation of all possible 1:1 randomization scenarios will be performed and scenarios approved or rejected based on the balancing criteria. Validity will be checked and balancing criteria may be relaxed to ensure that the number of possible scenarios is not overly constrained, and that no two clusters are always or never assigned to the same arm; or conversely may be tightened to ensure a smaller number of possible scenarios.

**Table 2:** Factors chosen *a priori* to be balanced by restricted randomization

Balancing factor	Operational definition	Starting balancing criteria
Baseline STH prevalence	Prevalence of any STH by Kato-Katz, weighted by age.	1% absolute difference in mean prevalence
Age distribution	Proportion of the cluster population that are eligible for treatment in the standard of care arm (ages 1-19)	1% absolute difference in mean proportion eligible
Socio-economic status	Proportion of households with dirt floors (earth, dirt, dung)	1% absolute difference
WASH access	Proportion of households reporting no access to a toilet facility	1% absolute difference
Urban / rural designation	Cluster defined as urban or peri-urban by DeWorm3 Site Team	1 cluster difference
Total population	Total number of individuals in each arm	5,000 individuals
Cluster area	In km  .	2.0 km 

Once a list of approved scenarios has been prepared, DeWorm3 Site Data Teams will select the final randomization scenario by a random method of their choosing, such as a second Stata program or a public

lottery. The final scenario will be shared with the Central DeWorm3 Data Team along with a report of the randomization procedure.

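### Objectives 1.1 and 2.1 rest on a by-site robust-variance GEE with 40 clusters, and the SAP names no small-sample method; the India region stratum is also missing from the model

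*SAP*

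**What the plan says.** SAP 6.2.1 specifies "generalized estimating equations with Poisson family, with robust variance estimation and exchangeable correlation matrix" for Objective 1.1, adjusted for the ten covariates of Table 5. SAP 6.2.2 uses the same model for Objective 2.1. On the unit of analysis, SAP 6.2 says "All analyses will be conducted separately for each site, unless otherwise specified", and SAP 3.1 says "At each site, 40 clusters are randomized", so each model has 20 clusters per arm. SAP 4.1 says that p-values below 0.05 "will indicate statistical significance for all analyses". The software section names R and SAS, without a procedure or option. Protocol section 7 adds nothing on small-sample inference.

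On allocation, SAP 3.2 describes randomisation "stratified by region in India (Jawadhu Hills, n=8 vs. Thimiri, n=32"). SAP 3.2.2 restricts it to secure "balance between arms in baseline population and in factors hypothesized to be strongly associated with STH transmission intensity", and its Table 2 lists seven balancing factors. Table 5 contains baseline cluster prevalence but neither India region nor urban/rural designation. On the latter, protocol section 7 says only "Models may be adjusted for baseline cluster-level STH prevalence and urban/rural designation", among other possible covariates.

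**The concern.** The ordinary robust (sandwich) variance is justified when the number of clusters is large. With 40 clusters it is biased downward, and a normal reference ignores the uncertainty in the variance estimate. Both effects make p-values too small. The sample-size formula in SAP 3.3.1 allows for few clusters through its leading 1 + term, but the analysis section has no counterpart. Two analysts could follow this SAP faithfully and report different p-values for a primary objective.

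A second, separate issue works in the other direction. When allocation is balanced on a factor that predicts the outcome and the model leaves it out, the estimated variance includes variation that the design has removed. The test then becomes conservative and power is lost. India's region stratum is the clearest candidate.

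**Working it through.** **Inputs.** From the SAP: 20 clusters per arm, m = 1,000 at endline, ICC 0.003-0.005, two-sided alpha 0.05, intervention prevalence 2%. Assumed, because the documents give no values: how strongly baseline prevalence or region predicts endline cluster prevalence.

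**1. The plan's own figures.** Solving the SAP 3.3.1 formula for control prevalence at 80% power gives 2.89% (ICC 0.003, c = 20, m = 1,000) to 3.44% (ICC 0.005, c = 15, m = 500). This agrees with the stated 3-3.5% to rounding. Simulated power at 7% and 10% versus 2% was 100%, consistent with the stated 98% or more.

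**2. Rejection rate with the ordinary sandwich and 1.96.** With p cluster-level parameters, the uncorrected variance is about (40 - p)/40 of the unbiased one, so the true rate is about P(|t on 40 - p df| > 1.96 × √((40 - p)/40)):

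- p = 2 (intercept, arm): P(|t38| > 1.910) = 6.4%
- p = 3 (plus baseline prevalence): P(|t37| > 1.885) = 6.7%
- p = 4 (plus one more, such as region): P(|t36| > 1.859) = 7.1%

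Null simulations (beta-binomial clusters, Poisson log-link GEE, prevalence 2% or 7%) gave:

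- arm only: 6.3-6.7%
- plus baseline prevalence: 6.9-7.2%
- all ten Table 5 covariates, with synthetic values: 6.6-7.6%
- three purely cluster-level covariates: 7.7-8.5%; five: 8.9-9.5%

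**3. Interval width.** The ratio of corrected to uncorrected width is t(0.975, 40 - p)/1.96 × √(40/(40 - p)):

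- p = 2: 2.024/1.96 × √(40/38) = 1.0597
- p = 3: 2.026/1.96 × √(40/37) = 1.0749
- p = 4: 2.028/1.96 × √(40/36) = 1.0907

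Uncorrected intervals are therefore too narrow by 1 - 1/1.0597 = 5.6%, 7.0% and 8.3%.

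**4. Effect of a correction.** With none or one cluster-level covariate, Kauermann-Carroll with a t reference rejected 4.8-5.3%, and Mancl-DeRouen with a normal reference 4.7-5.5%. A t reference alone, on the ordinary sandwich, left 5.4-6.4%.

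**5. India, region omitted.** Allocation stratified 8/32, prevalence 2%, baseline prevalence in the model but carrying no regional contrast, ordinary sandwich with 1.96. By assumed share of endline between-cluster variance explained by region:

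- 0%: 6.8-7.3%
- 10%: 5.9%
- 20%: 4.5-4.7%
- 30%: 3.1-3.7%

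Baseline prevalence may itself differ by region. With the endline share kept at 30%, and region explaining 30-80% of baseline variance, the rate was 4.9-7.0%. Over a wider grid with the same regional prevalence ratio (1.5 to 3) at baseline and endline it was 5.0-8.8%, mostly below 8%. Where the endline contrast exceeded the baseline one it was 0.6-6.5%.

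With region in the model, the ordinary sandwich gave 7.3-8.0%, Kauermann-Carroll with t on 36 df 5.1-5.7%, and a randomisation test over the stratified allocations 4.6-5.0%. Correcting the variance without adding region gave 2.1-2.5% at the 30% share with no baseline contrast, so the two changes belong together.

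**6. Where it matters.** At 3% versus 2%, ICC 0.005:

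- V = (0.0291 + 0.0196) × (1 + 999 × 0.005)/1,000 = 0.000292
- z = √(19 × 0.01²/0.000292) = 2.55
- power = Φ(2.55 - 1.96) = 72.3%

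A noncentral t on 36-38 df gives 72.1-72.3%. At 3.5% versus 2% the figures are 95.5% and 95.4-95.5%. At 7% versus 2% the same formula gives z = 9.7, where no choice of reference matters.

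**The case against.** Several points on the other side have force.

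- **This is an unspecified detail, not a wrong method.** A reader might infer that the SAP prescribes the uncorrected sandwich with 1.96. It does not; it is silent. What stands is that a primary analysis should not leave this open.
- **Table 5 already covers much of the balancing.** A reader might infer that omitting region drives India's error rate down to 3-4%. The documents do not support that as a general statement, because Table 5 adjusts for baseline cluster prevalence. The fall to 3-4% needs region to predict endline prevalence beyond baseline prevalence, and the documents do not say whether it does.
- **Urban/rural is not clearly an oversight.** The protocol lists it only as a possible covariate. The SAP then fixed a definite list that includes population density around the household, a plausible proxy. Age, socioeconomic status and water and sanitation access also have counterparts in Table 5.
- **The excess is small.** It is about 1-3 percentage points, and at the SAP's plausible control prevalences of 7-10% the conclusion would not change. This limits the weight of the point but does not remove it, because SAP 3.3.1 also works with detectable differences of 3-3.5% versus 2%.
- **The choice of correction is partly preference.** Mancl-DeRouen performs comparably. The essential step is to name one method.

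**Conclusion.** The point holds as an omission that should be repaired before the endline analysis. If the ordinary sandwich is used with a normal reference, the nominal 5% tests for Objectives 1.1 and 2.1 reject about 6-8% at each site, and intervals are about 6-8% too narrow. The rate is higher with several purely cluster-level covariates, so 8% is not a ceiling. Only borderline results are affected.

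The missing India stratum is a second, conditional point. It makes the test conservative only if region predicts endline prevalence beyond baseline prevalence. The 3-4% figure belongs to one assumed case: region explains 30% of endline between-cluster variance and baseline prevalence carries no regional contrast. It is not a floor either. If baseline prevalence carries the contrast, the rate stays at about 5-8%.

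The variance shares and covariate distributions are assumptions. The full seven-factor restriction and unequal cluster sizes were not simulated. The between-arm test of cluster proportions in Objective 1.2 uses Fisher's exact test and is not affected.

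**What to change.** In SAP 6.2.1 and 6.2.2, prespecify one method for both p-values and confidence intervals:

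- a bias-corrected sandwich, such as Kauermann-Carroll, with a t reference on 40 minus the number of cluster-level parameters (37 with intercept, arm and baseline prevalence; 36 in India once region is added); or
- a randomisation test over the approved restricted, stratified allocations of SAP 3.2.2, with intervals obtained by inverting the test.

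Add the region stratum to Table 5 for India. State whether urban/rural designation is included; if it is, the degrees of freedom fall by one more.

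The cost is a sentence in each section and one table row. Intervals become wider than uncorrected ones by 6.0% (arm only), 7.5% (plus baseline prevalence) and 9.1-10.0% (India with region). Planned power is essentially unchanged, because the leading 1 + in the sample-size formula already allows for few clusters. In the assumed India case with a 30% region share, adding region to the corrected test raised power at 3% versus 2% from 73.6% to 84.9%.
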